4.2.2 Patient Contact Form and Medical Record Release

After signing the consent, patients will be asked to complete a contact form providing their address, phone number, and email address, as well as the best time to reach them. They will also be asked to provide this information for alternate contacts, at least one of which is not related to them. This information will be used to facilitate the 6- and 12-week follow-up phone calls by the DCRI Call Center. Additionally, a medical record release form will be collected for use in the event that the DCRI Coordinating Center needs to collect medical records or bills for the 12-weeks health service utilization assessment.

Copies of the completed patient contact form and medical record release form will be faxed to the DCRI Call Center within 1 business day of randomization. If a patient's surgery date is unknown at the time of consent, a patient contact form and medical record release may still be completed, but randomization should be postponed. All documents should be held at the site until a surgery date is selected, at which time randomization may occur and documents may be submitted to the DCRI Call Center. The original documents will be retained by the site and stored either on paper or electronically in a secure location, according to the site's IRB-approved procedures.

4.2.3 Patient-Reported Baseline Assessments

Each patient will complete following assessments at baseline, during the pre-op visit or study enrollment visit. These assessments must be completed at least 10 days prior to the patient's surgery date:

- Surveys regarding health (KOOS, PROMIS Global Health, Satisfaction with Physical Function Scale)
- Physical activity
- Falls and hospitalizations in the prior 3 months
- Comfort with using technology
- Self-selected personal goal for recovery

Copies of the completed patient-reported baseline assessments will be faxed to the DCRI Call Center within 1 business day of randomization. If a patient's surgery date is unknown at the time of consent, baseline assessments may still be completed, but randomization should be postponed. All documents should be held at the site until a surgery date is selected, at which time randomization may occur and documents may be submitted to the DCRI Call Center. The original documents will be retained by the site and stored either on paper or electronically in a secure location, according to the site's IRB-approved procedures.

4.2.4 Baseline Case Report Form

The following patient data will be collected:

- Socio-demographic information
- Medical history and comorbidities
- Vital signs (heart rate, blood pressure, 10m gait speed) including height and weight

4.2.5 Patient Diary

Sites will be provided copies of a diary form to be given to each patient after randomization, as a method to support recall of healthcare interactions during the 6- and 12-week follow-up interviews. Patients will be instructed to use the diary to collect any interactions with the healthcare system that occur after they are discharged from the hospital following their surgery. Encounters of interest will include in-person PT visits, doctor visits, phone calls or emails to a PT or doctor, visits to an urgent care center or emergency room, and hospitalizations. Patients will also be instructed to rate weekly (on Sunday) their level of achievement of their self-selected

personal recovery goal. Data recorded on the diary will be collected from the patient verbally by the DCRI Call Center during the planned follow-up interviews.

4.3 Surgical Hospitalization and Discharge

Within two days of the scheduled surgery date, site coordinators will confirm the dates of admission and surgery, and enter these in the DCRI Registry System on the discharge data collection form. This will enable the DCRI Coordinating Center to confirm follow-up by the study therapist for intervention patients, and timing of outcome assessments for all patients. When confirming admission and surgical dates, the site coordinator also should confirm the expected discharge plan for all study patients to be a discharge home, and coordinate with hospital discharge planners to ensure that intervention patients are not referred to home health or outpatient PT.

Prior to hospital discharge, patients will be assessed for gait speed, pain, and falls during the hospitalization. While these are standard physical assessments, site coordinators may need to coordinate collection of these in-hospital data with the hospital team and inpatient physical therapist, to ensure they are captured for all study patients. The study coordinator is expected to enter these data on the discharge data collection form in the DCRI Registry System within 3 calendar days of hospital discharge. DCRI may also send an email to study staff within 1 business day of the original surgery date to confirm whether or not the surgery occurred.

Study staff should also coordinate with hospital staff, or develop an alternate method, to remind patients to begin completing their diary of healthcare encounters after discharge.

4.4 6 Weeks Post-Op

Standard clinical follow-up for TKR patients occurs approximately 6 weeks after surgery. At this routine visit, patients will be administered standard assessments for gait speed and range of motion (ROM) in the operated knee. Study coordinators may need to coordinate with the clinic team to ensure these data are documented consistently in the medical record.

The study coordinator is expected to enter these data on the 6-week data collection form in the DCRI Registry System within 14 calendar days of the visit.

At approximately 6 weeks after surgery, the patient will also be contacted by the DCRI Call Center to collect the following data via telephone interview. The interview is expected to last 20-30 minutes:

- Survey regarding health (KOOS)
- Adherence to prescribed PT regimen
- Pain
- Physical activity
- Falls since hospital discharge
- Healthcare encounters since hospital discharge, and weekly status of personal recovery goal (patient diary entries)

4.5 12 Weeks Post-Op

At approximately 12 weeks after surgery, the patient will be contacted again by the DCRI Call Center to collect the following data via telephone interview. The interview is expected to last approximately 20 minutes:

- Surveys regarding health (KOOS, PROMIS, Satisfaction with Physical Function)
- Adherence to prescribed PT regimen
- Physical activity
- Falls since last interview
- Healthcare encounters since last interview, and weekly status of personal recovery goal (patient diary entries)
- Thoughts about the tele-rehab platform (intervention patients only)

Also at 12 weeks after surgery, select sites may be asked to provide a summary of enrolled patients' outpatient clinic encounters (phone, email, in person) with orthopedic staff and physical therapists. This may be used to validate patient-reported encounters from the diary. Collection of the information, if requested, may be facilitated using the medical record release form signed by the patient at the time of enrollment.

5. Statistical Methods

The goal of this study is to assess the cost of the episode of care for total knee replacement, and whether the use of a tele-rehab platform is successful in mitigating some of those costs. The episode for analysis will be from surgery through 3 months post-discharge, in alignment with the new Comprehensive Care for Joint Replacement (CJR) bundled payment model being piloted by the Centers for Medicare and Medicaid Services (CMS). This will be a time-driven activity-based cost (TDABC) analysis. DCRI will be responsible for regular reporting of enrollment statistics, data quality, and data query status to the sponsor.

In addition to assessing the primary objective of cost, the study also will assess standard clinical measures of recovery (range of motion, gait speed) and qualitative measures of patient perceptions regarding their health and functional status (patient surveys) using both standardized and non-standardized tools. These assessments are intended to demonstrate the non-inferiority hypothesis that patients receiving PT via the tele-rehab platform did not have worse outcomes than patients receiving traditional in-person PT.

5.1. Sample Size

The primary aim of this study is to assess the difference in outpatient post-surgical costs between the control and intervention groups. The exact post-procedure cost estimates under study are unknown; however, we can estimate that an effect size of approximately 0.33 can be detected with 150 subjects per group with at least 80% power. The effect size is the ratio of the mean difference over the standard deviation (SD) assumed for each population, while the coefficient of variation (CV) is the ratio of the population mean over the SD. Lower variability would enable detection of a smaller cost difference, or the detection of a larger difference with fewer patients. The below table gives several mean ratios that could be detected with 80% power and 300 subjects where R1 is the ratio of the means (Control / Intervention) at which the power is calculated using a two-sample t-test with equal variance and a significance level of 0.05.

Power	N1	N2	N	R0	R1	Effect		
						Size	CV	Alpha
0.8023	150	150	300	1.000	1.033	0.3255	0.1	0.050
0.8070	150	150	300	1.000	1.067	0.3275	0.2	0.050
0.8003	150	150	300	1.000	1.100	0.3247	0.3	0.050
0.8045	150	150	300	1.000	1.134	0.3264	0.4	0.050
0.8184	150	150	300	1.000	1.170	0.3324	0.5	0.050
0.8101	150	150	300	1.000	1.200	0.3288	0.6	0.050
0.8078	150	150	300	1.000	1.230	0.3278	0.7	0.050
0.8096	150	150	300	1.000	1.260	0.3286	0.8	0.050
0.8143	150	150	300	1.000	1.290	0.3306	0.9	0.050
0.8209	150	150	300	1.000	1.320	0.3335	1.0	0.050
0.8098	150	150	300	1.000	1.340	0.3287	1.1	0.050
0.8025	150	150	300	1.000	1.360	0.3256	1.2	0.050
0.8153	150	150	300	1.000	1.390	0.3310	1.3	0.050
0.8125	150	150	300	1.000	1.410	0.3298	1.4	0.050
0.8116	150	150	300	1.000	1.430	0.3295	1.5	0.050
0.8123	150	150	300	1.000	1.450	0.3297	1.6	0.050
0.8004	150	150	300	1.000	1.460	0.3247	1.7	0.050
0.8039	150	150	300	1.000	1.480	0.3262	1.8	0.050
0.8082	150	150	300	1.000	1.500	0.3280	1.9	0.050
0.8007	150	150	300	1.000	1.510	0.3248	2.0	0.050

Thus, with 300 subjects we can detect an effect size of 0.33 which represents a whole scenario of cost differences that can be detected with at least 80% power that is dependent on the variability of the costs under study. The below table illustrates some example cost differences that could be detected based on the assumed SD of the costs.

Standard Deviation (SD)	Mean Cost Difference (\$)	Standard Deviation (SD)	Mean Cost Difference (\$)
100	32.50	800	259.60
200	64.90	900	292.10
300	97.40	1000	324.50
400	129.80	1100	357.00
500	162.30	1200	389.50
600	194.70	1300	421.90
700	227.20	1400	454.40
750	243.40	1500	486.80

If the mean cost difference expected is around \$500, then the SD should be no more than \$1500 in order to maintain at least 80% power. If the cost difference is around \$200 then the SD would need to be no more than \$600.

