5.2. Data Analyses

Data will be analyzed as intent-to-treat, therefore all randomized patients will be included for analysis as randomized, regardless of whether or not they completed all protocol requirements. The exception will be if a patient withdraws consent to participation and requests in writing that all data previously collected be removed from the study.

Baseline patient demographics, clinical characteristics, and outcomes assessed at each time point will be summarized overall and for each group. Continuous variables will be summarized using the mean, SD, median, inner-quartile range (IQR) and range, while categorical variables will be presented using counts and percentages. The primary cost comparisons will be done using a t-test if data are normally distributed or can be normalized using a transformation such as the logarithm or square root, otherwise, the nonparametric Wilcoxon Rank sum test will be used.

All analyses will be completed using SAS version 9.4 or higher, and a p-value < 0.05 will be considered statistically significant. A detailed statistical analysis plans will be prepared prior to analyses.

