9.9 Power and Sample Size Calculations

The primary aim of this study is to assess the difference in outpatient post-surgical costs between the control and intervention groups at 12-weeks post-operative. The exact post-procedure cost estimates under study are unknown; however, we can estimate that an effect size of approximately 0.33 can be detected with 150 subjects per group with at least 80% power. The effect size is the ratio of the mean difference over the standard deviation (SD) assumed for each population. Lower variability would enable detection of a smaller cost difference, or the detection of a larger difference with fewer patients. The sample size estimates were made assuming a two-sample t-test with equal variance and a significance level of 0.05. Thus, with 300 subjects we can detect an effect size of 0.33 which represents a whole scenario of cost differences that can be detected with at least 80% power that is dependent on the variability of the costs under study. The below table illustrates some example cost differences that could be detected based on the assumed SD of the costs.

Standard Deviation (SD)	Mean Cost Difference (\$)	Standard Deviation (SD)	Mean Cost Difference (\$)
100	32.50	800	259.60
200	64.90	900	292.10
300	97.40	1000	324.50
400	129.80	1100	357.00
500	162.30	1200	389.50
600	194.70	1300	421.90
700	227.20	1400	454.40
750	243.40	1500	486.80

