The null hypothesis for the primary endpoint is that there is no treatment difference between patients who receive tele-rehab-supported PT versus traditional home and/or clinic-based PT. The alternative hypothesis is that a treatment difference exists between patients who receive tele-rehab-supported PT versus traditional home and/or clinic-based PT.

Let μ_T and μ_C be the average total health care costs for the virtual and control PT groups, respectively. The null hypothesis and the alternative hypothesis will be as follows:

$$\begin{aligned} H_0: \mu_T &= \mu_C \\ H_A: \mu_T &\neq \mu_C \end{aligned}$$

The primary statistical method for the hypothesis test will be t-test, and the mean difference between groups will be presented with a 95% confidence interval (CI). The test is two-sided even though we are more interested in determining that the intervention group is superior to the control group to allow for a possible negative significant difference.

Let \bar{X}_T and \bar{X}_C be the sample mean costs for the virtual and control groups, respectively, and let S_T^2 and S_C^2 be the sample variance for the virtual and control samples, respectively. The equality of the variances of the two samples will be tested using the Folded F-test (i.e., $F = \text{Max}(S_T^2, S_C^2)/\text{min}(S_T^2, S_C^2)$). If there is not strong statistical evidence to say that the variances of the two samples are different (insignificant F-test and 4-fold variance difference), then the alternative hypothesis for total cost will be concluded when the associated t-test statistic assuming equal variance is less than the 2.5th percentile of the Student's t distribution with $n_T + n_C - 2$ degrees of freedom, where n_T is the number of subjects in the virtual group and n_C is the number of subjects in the control group. Otherwise, the t-test will be computed assuming the variances are unequal.

If a parametric method is determined not to be possible through normality checks (Shapiro-Wilks test) or transformations, a Wilcoxon rank-sum test will be performed for the primary effectiveness endpoint and a 95% CI for the median difference presented.

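### Does the upside-down definition of the coefficient of variation in Protocol 5.1, with a log scale left unnamed, undermine the sample size?

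*Protocol*

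**What the plan says.** Protocol 5.1 assumes 150 patients per group and at least 80% power. It defines the effect size on the scale of the data: "The effect size is the ratio of the mean difference over the standard deviation (SD) assumed for each population". The same sentence adds that "the coefficient of variation (CV) is the ratio of the population mean over the SD". The ratio table follows, with one CV per row from 0.1 to 2.0. In it, "R1 is the ratio of the means (Control / Intervention) at which the power is calculated using a two-sample t-test with equal variance", at a significance level of 0.05. The section then continues: "Thus, with 300 subjects we can detect an effect size of 0.33 which represents a whole scenario of cost differences". A second table gives detectable dollar differences for assumed SDs from $100 to $1,500.

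No log scale is mentioned in 5.1. The logarithm first appears in Protocol 5.2, where the t-test is used if costs are normal or "can be normalized using a transformation such as the logarithm or square root", with the Wilcoxon rank-sum test otherwise. SAP 9.10 keeps that sequence.

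SAP 9.9 restates the sample size with the dollar table alone: "The sample size estimates were made assuming a two-sample t-test with equal variance and a significance level of 0.05". It has neither the CV clause nor the ratio table.

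**The concern.** Two things look wrong. First, the CV is defined as its own reciprocal, and the table contradicts that definition. If CV were mean over SD, a larger CV would mean relatively less variable costs and the detectable ratio should fall down the table. The printed R1 rises from 1.033 to 1.510.

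Second, putting the CV the right way up does not rescue the derivation on the dollar scale. Mean difference over SD then gives 0.2550 at CV 2.0, against a printed 0.3248.

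If the printed effect sizes were wrong, the claim of 80% power would lose part of its support. The primary comparison would then be less well powered than stated when costs are highly variable. The worry is sharper because the SAP states the primary hypothesis in terms of mean costs, and because the ratio table is followed directly by a dollar table on the raw scale.

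**Working it through.** **Inputs (Protocol 5.1).** 150 per group, significance level 0.05, two-sample t-test with equal variance, and the printed R1, CV, effect size and power in each row. Section 5.1 does not state sidedness. SAP 9.10 makes the test two-sided, and two-sided reproduces the table.

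**Step 1: effect size to power.** I used the noncentral t with 298 degrees of freedom and noncentrality d × √(150/2). Each printed effect size returns its printed power to within 0.0002 in all 20 rows. An effect of 0.33 gives 81.3%. Exactly 80% needs d = 0.32455.

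**Step 2: R1 and CV to effect size.** Three readings:

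- log scale, CV = SD/mean: d = ln(R1) / √ln(1 + CV²)
- raw scale, CV = SD/mean, SD = CV × intervention mean: d = (R1 − 1) / CV
- raw scale, CV = mean/SD as worded: d = (R1 − 1) × CV

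| CV | R1 | Printed d | Log scale | Raw, SD/mean | Raw, mean/SD |
|---|---|---|---|---|---|
| 0.1 | 1.033 | 0.3255 | 0.3255 | 0.3300 | 0.0033 |
| 0.5 | 1.170 | 0.3324 | 0.3324 | 0.3400 | 0.0850 |
| 1.0 | 1.320 | 0.3335 | 0.3335 | 0.3200 | 0.3200 |
| 1.5 | 1.430 | 0.3295 | 0.3295 | 0.2867 | 0.6450 |
| 2.0 | 1.510 | 0.3248 | 0.3248 | 0.2550 | 1.0200 |

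Worked example at CV 1.0: ln(1.320) = 0.2776, √ln 2 = 0.8326, and 0.2776 / 0.8326 = 0.3335.

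Over all 20 rows the log formula matches every effect size and every power to four decimals. Neither raw-scale reading matches any row. The log formula with CV inverted matches only at CV 1.0, where a number and its reciprocal coincide.

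**Step 3: direction check on the definition.** With CV as mean/SD on the raw scale, the ratio detectable with 80% power is 1 + 0.32455/CV. That is 4.25 at CV 0.1 and 1.16 at CV 2.0, a falling series where the printed one rises. So the words are inverted and the numbers are not.

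**Step 4: the dollar table.** This is 0.32455 × SD: $324.5 at SD $1,000 and $486.8 at SD $1,500, as printed. The two worked examples, $500 with SD $1,500 and $200 with SD $600, are both d = 0.333, about 82% power. None of this uses a CV.

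**Step 5: does the planned analysis deliver the printed power?** Costs were simulated as lognormal with equal CV in both groups at the printed R1, with 20,000 replicates for the t-tests and 4,000 for Wilcoxon:

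| CV | Printed | Log t-test | Wilcoxon | Raw t-test |
|---|---|---|---|---|
| 1.0 | 82% | 82% | 81% | 68% |
| 1.5 | 81% | 81% | 80% | 57% |
| 2.0 | 80% | 80% | 78% | 50% |

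The two routes that the plan names for skewed costs hold the printed power to within about 2 points.

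**The case for a change.** The best case for a correction is that the table invites a raw-scale reading. Section 5.1 describes R1 as a ratio of means and the effect size as a difference over the SD. SAP 9.10 states its hypothesis on mean costs, and SAP section 5 makes the protocol the definitive reference, so leaving the table out of SAP 9.9 does not correct it. Read on the raw scale with SD equal to CV times the intervention mean, the printed ratios give 79%, 70% and 60% power at CV 1.0, 1.5 and 2.0. At CV 2.0, 80% power would need a ratio of 1.649.

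High CVs are also plausible. SAP 9.10 assigns $600 to the intervention, $150 to a doctor's visit and $7,825 to a re-hospitalization. Assume, purely for illustration, two doctor's visits each, 2% to 5% of intervention patients re-hospitalized once, and nothing else. At 2% the mean is 600 + 300 + 0.02 × 7,825 = $1,056.50 and the SD is 7,825 × √(0.02 × 0.98) = $1,095, a CV of about 1.0. At 5% the CV is about 1.3.

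What stands is that the definition is inverted and the scale is unlabelled. The claimed loss of power does not stand as a fault in the table:

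- The table pairs a single CV per row with equal variance. When the means differ, both can hold together on the log scale but not on the raw scale.
- An untransformed t-test on strongly skewed costs is not the route that either document chooses.
- The sentence linking the two tables claims only that an effect size of 0.33 is detectable, which is true on whichever scale the test is run.

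Whether a log-scale or rank test properly answers a question about mean cost is a separate matter of analysis, and this table does not settle it.

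**Conclusion.** The concern is right about the wording, but it has no consequence for the plan. One definition is upside down and one table lacks a scale label. A statistician who sees R1 rise with CV will read CV as SD over mean, and the log formula then returns every row exactly.

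No printed effect size or power changes. The 300 patients, the 0.33 effect size, the dollar table, the worked examples, the analysis and SAP 9.9 all stay as they are. Replacing the table with raw-scale ratios would gain nothing: it would swap a correct calculation for one that assumes near-normal costs at CVs where non-negative costs cannot be near-normal.

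Two assumptions remain. The log scale is inferred from the match on all 20 rows, since the documents do not state it. The printed power for a given ratio also relies on roughly lognormal costs with similar CV in the two groups. The documents give no expected CV and rely on no particular row of the table, so no design decision turns on it.

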5.2. Data Analyses

Data will be analyzed as intent-to-treat, therefore all randomized patients will be included for analysis as randomized, regardless of whether or not they completed all protocol requirements. The exception will be if a patient withdraws consent to participation and requests in writing that all data previously collected be removed from the study.

Baseline patient demographics, clinical characteristics, and outcomes assessed at each time point will be summarized overall and for each group. Continuous variables will be summarized using the mean, SD, median, inner-quartile range (IQR) and range, while categorical variables will be presented using counts and percentages. The primary cost comparisons will be done using a t-test if data are normally distributed or can be normalized using a transformation such as the logarithm or square root, otherwise, the nonparametric Wilcoxon Rank sum test will be used.

All analyses will be completed using SAS version 9.4 or higher, and a p-value < 0.05 will be considered statistically significant. A detailed statistical analysis plans will be prepared prior to analyses.

